5. MATERIAL & METHODS

It is an open label randomized control trial. It will be done in ILS Hospital, Kolkata for a trial period of around 3 years.

Diabetic patients attending the foot clinic with plantar ulcer irrespective of age, sex, glycemic control, duration of diabetes, duration of ulcer and presence of infection will be considered for the study. At first patients will be randomly allocated to any one of two off-loading procedures using the randomization table: TCC or PSC. Those who will refuse TCC, will be shifted to PSC group. All patients will be followed up at the foot clinic once in two weeks' basis for device inspection, wound care and wound debridement as and when indicated. After the completion of treatment, all the patients will be followed up to 15 months from the initiation of treatment to identify any recurrence of ulcer.

Two outcome measures will be used. The primary outcome measure is healing of the ulcer after 8 months. The secondary outcome measure is to document which of the device is associated with comparatively better healing at 6 months.

6. OUTLINE OF TIME PLANS:

Proposed date of starting research activity: January 2023

Expected duration of research activity: 1.5 years

Undertaking to provide interim report of the work halfway through it: Yes

Undertaking to provide full report of the work on completion: Yes

7. STATISTICAL ANALYSIS:

Comparison will be done between the two groups. Continuous variables will be compared by t-tests and categorical variables by chi-square test. Baseline comparison will be made using chi-square tests and two-sample t-tests. Continuous variables will be expressed as mean (standard deviation). The differences in pertinent characteristics will be established with the use of t-test for independent samples. A two-sided p value of 0.05 was considered statistically significant.

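### The healing comparison uses no baseline variable: a prespecified analysis stratified by Wagner grade would handle chance imbalance in grade at little cost, though the gain is small and the planned test is not biased

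*Combined protocol and SAP*

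**What the plan says.** Section 7 (Statistical Analysis) is the whole analysis plan. For outcomes it states: "Continuous variables will be compared by t-tests and categorical variables by chi-square test". For baseline it states: "Baseline comparison will be made using chi-square tests and two-sample t-tests", and "Continuous variables will be expressed as mean (standard deviation"). It sets a two-sided 0.05 level. It names no regression, stratified test or covariate, and nothing follows from a baseline difference once one is found.

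Section 5 (Material & Methods) makes healing after 8 months the primary outcome, read here as healed or not, so the chi-square test applies. Allocation is "using the randomization table: TCC or PSC", with no stratification stated. Section 4 admits Wagner grade 2 or 3, and section 5 takes patients "irrespective of age, sex, glycemic control, duration of diabetes, duration of ulcer and presence of infection". The history form in section 12 has fields for Wagner grade, ulcer duration and ulcer size.

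Two further statements bear on the point. Section 5 says "It is an open label randomized control trial", and of patients who decline the cast, "Those who will refuse TCC, will be shifted to PSC group". No analysis set is defined.

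**The concern.** Entry is deliberately broad, and grade is the one severity measure used to select patients. If grade predicts healing, two things follow from ignoring it. The treatment difference is estimated with somewhat more variance than necessary. And if the arms happen to differ in their share of grade 3 ulcers, part of the observed difference in healing reflects grade, and the plan gives no agreed way to take that into account.

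The baseline tests do not fill the gap, because a material imbalance can be non-significant in a trial of modest size. Any adjustment improvised later, in an open-label trial, would look chosen after the result. The stake is how an imbalanced trial is read, plus a small amount of power.

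**Working it through.** **Inputs.** From the documents: two arms, two-sided 0.05, binary healing at 8 months, grades 2 and 3, no stated stratification. The documents state no sample size, healing rate or prognostic strength, so there is no figure of theirs to reproduce. The rest is assumed: 60 or 25 per arm, equal allocation, 40% grade 3, analysis as randomised.

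**Step 1: how often grade is imbalanced.** The SD of the difference in grade 3 share is sqrt(2q(1−q)/n).
- n = 60: sqrt(2×0.4×0.6/60) = 0.0894. Fifteen points is 9 patients; with a half-patient correction, (8.5/60)/0.0894 = 1.58, two-sided probability about 11%.
- n = 25: sqrt(0.48/25) = 0.1386. Fifteen points is 3.75 patients, so 4 or more; (3.5/25)/0.1386 = 1.01, probability about 31%.

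**Step 2: what a baseline test would show.** A 15-point difference gives z = 0.15/0.0894 = 1.68 (p about 0.09) at 60 per arm and 0.15/0.1386 = 1.08 (p about 0.28) at 25. With 30–50% grade 3 the ranges are 0.07–0.10 and 0.25–0.29.

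**Step 3: precision.** The share of variance removed by adjusting for grade is roughly R² = q(1−q)(p2−p3)²/[p(1−p)], where p2 and p3 are healing rates in grades 2 and 3 and p is overall healing. With q = 0.5:
- 90% v 80% (odds ratio 9/4 = 2.25): 0.0025/0.1275 = 2%; interval about 1% narrower.
- 90% v 70% (odds ratio 9/2.33 = 3.9): 0.01/0.16 = 6%; about 3% narrower.
- 90% v 50% (odds ratio 9/1 = 9): 0.04/0.21 = 19%; about 10% narrower.

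**Step 4: error and power by simulation.** Model: logit P(heal) = a + effect×arm + grade + duration + size, with a = 1 or 2 (reference healing 67–72% or 81–87%). Grade 3 log-odds are −0.7, −1.1 and −1.8 (odds ratios exp(0.7) = 2, exp(1.1) = 3, exp(1.8) = 6). These go with ulcer duration at −0.2, −0.47, −0.7 per SD and size at −0.47, −0.7, −1.0 per SD. The treatment log-odds effect is 0, −1.0 or −1.3. There are 40,000 trials per cell; the unadjusted chi-square test is set against a Mantel-Haenszel test stratified by grade.

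| | 60 per arm | 25 per arm |
|---|---|---|
| Grade imbalance of 15 points or more | about 11% of trials | about 31% |
| Type I error in those trials, unadjusted | about 5–9% | about 5.5–7.5% |
| Type I error in those trials, stratified | about 4–5.5% | about 4–5.5% |
| Change in power from stratifying | about 0 to +3 points | about −4 to +1 points |

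Simulation error in the imbalanced subsets is small: sqrt(0.07×0.93/4,400) = 0.4 points at 60 per arm and sqrt(0.065×0.935/12,400) = 0.2 at 25.

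**Step 5: the other trials.** Overall error of the unadjusted test is about 5%, so the excess is offset elsewhere. At the top of each range, the remaining trials reject in (5 − 0.11×9)/0.89 = 4.5% at 60 per arm and (5 − 0.31×7.5)/0.69 = 3.9% at 25.

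**Sensitivity.** If grade were the only predictor of healing, error in imbalanced trials at 60 per arm would reach about 11% at an odds ratio of 6. For a 20-point difference at 50 per arm, with half the ulcers grade 3, power would go from 60 to 61% with 90% v 70% healing, and from 54 to 61% with 90% v 50%. A larger gain therefore needs grade to be a very strong predictor.

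**The case against.** An unadjusted chi-square test on a randomised binary outcome is an accepted primary analysis. Its error is about 5% overall, and the imbalanced trials are a subset picked out after the fact. All of that stands, and it makes this an improvement rather than the correction of an error. It is equally true that the documents supply none of the inputs that set the size of the gain, and that stratification costs power if the trial is very small.

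Four stronger readings are tempting, and the documents do not support them.
- *The planned test is biased or inflates false positives.* It does not, if patients are analysed as randomised.
- *Adjustment would bring large power gains.* Gains such as 70 to 83% at 60 per arm can be produced, but only by also adjusting for ulcer duration and size and assuming strong effects for all three. Nothing in the text establishes those strengths.
- *Conditional error of 12–15%.* Such figures come from a single continuous predictor with an odds ratio of 2.7 to 4.5 per SD, a stronger assumption than the one used here.
- *The baseline tests act as a gatekeeper.* Section 7 gives them no such role. The fair criticism is only that they correct nothing.

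Timing may also limit the change. Section 6 proposes a January 2023 start, a duration of 1.5 years and a halfway report; section 5 has the trial running "for a trial period of around 3 years". Halfway is therefore 9 months in (October 2023) or 18 months in (July 2024). Section 10 cites a paper published on 21 August 2024, so the text postdates both. It does not say whether the report was made or what it showed, so one cannot conclude that outcome by arm has been seen.

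**Conclusion.** The point holds, at small size. Section 7 leaves grade out of the healing comparison although it is an entry criterion already on the form. The cost is a little precision and no protection when the arms differ on grade by chance. Stratifying brings type I error in such trials back to about 5%. Its effect on power is slight, and can be negative in a very small trial.

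This rests on assumed sample sizes, healing rates, a 40% grade 3 share and a grade odds ratio of 2 to 6, and on analysis by randomised arm. The last condition is not secured, because refusers of TCC move to PSC and no analysis set is defined. Stratifying by grade does not repair that. It and the absent sample size rank above this point.

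**What to change.** First establish whether outcome by arm has been tabulated.

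- **If not:** prespecify and date a primary analysis of healing at 8 months by randomised arm, stratified by Wagner grade (2 v 3). A Mantel-Haenszel test would serve, with the stratified risk difference Σw·d/Σw, where w = n1·n0/(n1+n0) and d is the difference in healing within each grade, and its 95% CI. Report the unadjusted chi-square test as supportive.
- **If so:** keep chi-square primary and label the stratified result post hoc.

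In either case, require Wagner grade to be recorded for every patient before device fitting, and replace the baseline significance tests with a descriptive table by randomised arm. Adjustment for ulcer duration and size can be a supportive analysis. Rules tying the number of covariates to event counts, and penalised fits, are not needed.

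The cost is a short paragraph in the SAP, one extra analysis, and up to about 4 points of power if the trial has only about 25 per arm.

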12. COPY OF HISTORY FILE

POSTERIOR SLAB VS TOTAL CONTACT CAST IN DIABETIC FOOT ULCERS: A RANDOMIZED CONTROLLED TRIAL

CASE REPORT FORMS TO BE FILLED AT THE TIME OF FIRST OP VISIT

DIABETES & OBESITY CLINIC (ASSESSMENT FORM)

Date.....

UHID No.

1. Patient Details :

Name :	Age :	Sex : Male / Female
Address :		
Marital Status :		Religion :
Phone Nos. :		Mobile No. :
Refd. By Dr. : Under Consultant Dr.		

2. Diabetic History :

Age of Onset :	Mode of Onset : Accidental / Others.....
Duration Of diabetes : Treatment Taken for DM :	

3. Family History of Diabetes.

Is anybody in the family is suffering from Diabetes : YES / NO
If Yes Father / Mother

PATERNAL					MATERNAL				
GF	GM	UNC	AUN	CS	GF	GM	UNC	AUN	CS

4. A Past Medical History :

	NATURE	SINCE WHEN	MEDICATIONS	PRESENT STATUS
Heart Disease				
Kidney Disease				
Liver Disease				
Asthma / COPD				
Hypertensions				
Chronic Infections				
Others				

B. Past History of Hospital Admission / Surgical History :

Reason	Treatment (Surgical / Conservative)	Dates

5. Present History of Diabetics :

A. Present Symptoms :

.....

.....

B. Treatment Receiving now :

OHA : _____

OHA + INSULIN : _____

INSULIN : _____

ALTERNATIVE MEDICINE : _____

NO MEDICINE : _____

C. Any Symptoms Of Hypoglycemia :

If YES HOSPITALISATION DOMESTIC TREATMENT

NO

D. Recent B. Sugar Values.....

Blood Sugar	Values	Date
RBS		
FBS		
PPBS		
HbA1c		
Others		

E. Complication of Diabetes :

	Present / Absent		Duration	Treatment received if any
Eye				
Kidney				
Heart				
Foot				
Nerves				
Others				

6. For Female Patient :

Gravida..... Parity..... H/O GDM.....

Gynecological Problems (If Any)

7. Physical Examination :

1. Height : **Weight :** , **BMI :** **EBW :**

2. Pulses : Rate : beats per min, Rhythm : Regular / Irregular

- Radial
- Brachial
- Carotid
- Femoral
- Dorsalis Pedis

3. Blood Pressure : Standing : mm of Hg; Supine mm of Hg

4. Thyroid : 5. Oedema :

6. Respiratory System :

7. Cardio Vascular System :

8. Abdomen :

9. Skin / Eyes :

10. Central Nervous System :

7. Cardio Vascular System :

9. Skin / Eyes :

10. Central Nervous System :

8. Investigation :

Type	Dates									
	1	2	3	4	5	6	7	8	9	10
BLOOD SUGAR										
FBS										
PPBS										
RBS										
Hb1Ac										
RENAL										
Urea										
Creat.										
Micro albumin										
24 Hr. Urine										
Protein										
Creatinine										
Clearance										
BLOOD LIPIDS										
Cholesterol										
Triglyceride										
HDL										
LDL										
VLDL										
LFT										
Bill (T)										
Bill (D)										
Bill (I)										
Protien										
Alb										
Glob										
SGOT										
SGPT										
Alk Ph.										
GGT										
Uric Acid										
HAEMOGRAM										
Hb%										
WBC										
DC										
ESR										
Plat.										
PCV										

Foot Examination :

Foot Examination

Right:

Right :
Left :

ERT :

VII.

Right.

Left : _____

Left :
Hot & C

Hot & Right

Right : _____

Left .

ABT
Right

DIABETES & OBESITY CLINIC

[figure not shown]
DATE	FOLLOW UP COMPLAINTS	TREATMENT ADVICE

NAME: AGE: SEX:

ADDRESS:

MOB.NO: REFERRING DR.:

MEDICAL HISTORY		DIABETIC FOOT HISTORY		
		RT	LT	
Duration of Diabetes		Duration of Ulcer		
Duration of Hypertension		Past H/O Ulcer		
Height		H/O Amputation		
Weight		Joint pain		
BMI		Stiffness		
Dyslipidemia		Dry skin		
SMOKER		Numbness		
CVD		Tingling/Pricking		
CKD		Paresthesia		
Blood Sugar		Claudication		
HbA1C		Cramping		
		Oedema		

[figure not shown]
[figure not shown]

EXAMINATION OF FOOT

INSPECTION

DRY SKIN	YES	NO	ABNORMAL SHAPE	YES	NO
FISSURE	YES	NO	NAIL LESION	YES	NO
DEFORMITY	YES	NO	LOSS OF HAIR	YES	NO
CALLUS	YES	NO			

PALPATION	HOT	COLD	NORMAL
RIGHT			
LEFT			
FOOT PULSES	RT	LT	
DORSALIS PEDIS			
POTERIOR TIBIALIS			
ASSESSMENT OF NEUROPATHY	RIGHT	RIGHT	LEFT
MONOFILAMENT			
VPT			
HCP			

[figure not shown]
[figure not shown]

VASCULAR ASSESSMENT	RIGHT	LEFT
DORSALIS PEDIS		
POSTERIOR TIBIALIS		
BRACHIALIS		
ABI		

RADIOLOGICAL INVESTIGATION (X RAY FOOT)

RT:-

LT:-

DESCRIPTION OF ULCER

Location :-

Size:-

Base:-

Margins:-

Depth:-

CLINICAL DIAGNOSIS			WEGNERS CLASSIFICATION	
	YES	NO	Grade-0	
NEUROPATH Y			1-Superficial Ulcer	
CHARCOT FOOT			2-Deep Ulcer	
PVD			3-Osteomyelitis	
INFECTED			4-Localized Gangrene	
OTHERS			5-Extensive Gangrene	

TREATMENT	YES	NO
Callus and Corn Removed		
Nail paring		
I+D done		
Pus for CS		
Probing		
Extensive debridement		
Surgical Referral		
Others		
OFFLOADING TECHNIQUE	YES	NO
S K OFFLOADING		
OFFLOADING SHOE		
TOTAL CONTACT CAST		
INSTANT TCC		
CUSTOM FOOTWEAR		
OTHERS		

FOLLOW UP

[figure not shown]
Specialised Medical Personnel Curriculum Vitae

Full Name:	[name]
Academic Title:	SENIOR CONSULTANT - DIABETOLOGIST
Present Position:	PRINCIPAL INVESTIGATOR
Business Address:	ILS Hospltd [name]
Relevant Education: (Type of degree and year when awarded)	MBBS-1984, MD-1988

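### Patients who refuse TCC after randomisation are counted as PSC in the comparison, and the first-visit form, as far as it can be read, does not by itself identify them

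*Combined protocol and SAP*

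**What the plan says.** Section 5 (Material & Methods) sets out the allocation: "At first patients will be randomly allocated to any one of two off-loading procedures using the randomization table: TCC or PSC". The next sentence gives the rule for refusal: "Those who will refuse TCC, will be shifted to PSC group". No corresponding rule moves patients from PSC to TCC. The primary outcome is ulcer healing after 8 months; the secondary outcome compares healing between devices at 6 months.

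Section 7 (Statistical Analysis) opens with "Comparison will be done between the two groups". It names t-tests and chi-square tests. It does not say whether patients are analysed by arm as randomised or by device received.

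Section 12 (Copy of History File) reproduces a form under the trial's own title, "POSTERIOR SLAB VS TOTAL CONTACT CAST IN DIABETIC FOOT ULCERS: A RANDOMIZED CONTROLLED TRIAL", with the instruction "CASE REPORT FORMS TO BE FILLED AT THE TIME OF FIRST OP VISIT". Under "OFFLOADING TECHNIQUE" it has a yes/no list of six rows: S K offloading, an offloading shoe, "TOTAL CONTACT CAST", an instant version of the TCC, custom footwear and a catch-all. No row names the posterior slab. The readable parts of the form contain no randomisation number, allocated arm, TCC refusal or device-change field. The form does carry a UHID number and a free-text follow-up sheet.

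**The concern.** Randomisation makes the two groups comparable at the moment of allocation. A refusal comes after that moment and is the patient's own choice. Patients who refuse a cast may differ from those who accept it in ulcer severity, mobility, adherence or other features related to healing. If they are counted with PSC, the TCC group keeps only those who accepted, while the PSC group holds all of its own patients plus the TCC refusers. A difference in healing could then reflect who chose which device.

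Refusal is foreseeable: section 2 describes TCC as poorly tolerated by patients, and section 5 writes a rule for it. The form matters because it is the only data-collection instrument in the documents. Without an arm or refusal field, it offers no direct way to undo the regrouping or to report how many patients crossed over.

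**Working it through.** The plan states no sample size, refusal rate or healing rate, so there is no figure of its own to reproduce. The check has three steps.

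**1. Who is in each group as written.** Section 5 calls the destination of refusers the PSC group. Section 7 compares the two groups without redefining them. Read together, the TCC group is those randomised to TCC who accepted it. The PSC group is those randomised to PSC plus those randomised to TCC who refused.

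**2. What the form records.** Suppose a PSC is ticked under the catch-all row, the only checklist row evidently open to it:

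| Patient | TCC row | Catch-all row | Arm field | Refusal field |
|---|---|---|---|---|
| Randomised to TCC, accepts | Yes | No | none | none |
| Randomised to TCC, refuses, receives PSC | No | Yes | none | none |
| Randomised to PSC | No | Yes | none | none |

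The last two lines are identical. Of the six rows, none names PSC and two name a form of TCC.

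**3. Size, for an assumed refusal rate r.** With 1:1 allocation (also assumed, since the ratio is not stated) and n patients per arm, the PSC group as written has n + rn patients, of whom rn are refusers. The share is rn/(n + rn) = r/(1 + r), whatever n is:

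- r = 10%: 0.10/1.10 = 9.1%
- r = 20%: 0.20/1.20 = 16.7%
- r = 30%: 0.30/1.30 = 23.1%

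To see how this reaches the outcome, suppose the two devices heal equally well. Let h_a be the healing proportion in patients who would accept TCC and h_f that in patients who would refuse it, with a fraction r of would-be refusers in each arm. The TCC group as written heals at h_a. The PSC group as written heals at [(1 − r)h_a + 2r·h_f]/(1 + r). The apparent difference, PSC minus TCC, is 2r(h_f − h_a)/(1 + r), although the true difference is zero. The multiplier 2r/(1 + r) is 0.18, 0.33 and 0.46 at r = 10%, 20% and 30%. By arm as randomised, both arms heal at (1 − r)h_a + r·h_f and the difference is zero, as it should be. The documents give neither h_f nor h_a, so neither the direction nor the size of the bias can be stated.

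**The case against.** The strongest objection is that the randomised arm may be recoverable without the form. Section 5 refers to a separate randomisation table, and the form's UHID number could link the two. A patient listed as TCC in the table but with no TCC tick would then be flagged as a possible refuser. This stands as far as it goes. A reader might infer from the form that refusers can never be told apart from patients randomised to PSC; the documents do not support that. Equally, they do not say that the table is kept as a patient-level list, linked to the form or used in the analysis, so the loss is a risk and not a demonstrated fact.

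Second, the form is a first-visit document and several parts of it are not shown in the public copy, including the area after its follow-up heading. PSC could also be written in free text. This limits any claim of absence to the readable fields. The offloading checklist, however, is readable, and neither the catch-all row nor the free-text sheet prompts for allocation or refusal.

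Third, the bias comes from the regrouping rule and the undefined analysis population, not from a missing tick-box. This is correct. A perfect form would leave the bias in place, whereas an analysis by randomised arm with a retained list would largely remove it even with the present form. The form is therefore the supporting part of the point.

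Fourth, the percentages only restate an assumed refusal rate. That is also correct, and they should be read that way.

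**Conclusion.** The point holds in this form: as sections 5 and 7 are written, TCC refusers are analysed as PSC, so the comparison of healing is open to bias from one-directional self-selection. The readable first-visit form does not by itself allow those patients to be identified. The first part rests on the natural reading of the two sections together, since section 7 offers no other definition of the groups. The second rests on the readable fields only.

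The size is unknown. The 9% to 23% range depends on assumed refusal of 10% to 30% and 1:1 allocation. Bias arises to the extent that refusers differ from accepters in their chance of healing. The documents do not show that any patient's allocation has been or will be lost. The matter still deserves a change, because it affects the primary outcome and is cheap to correct.

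**What to change.** - In section 7, state that the primary comparison is by arm as randomised, with TCC refusers kept in the TCC arm for analysis whatever device they receive. Present a comparison by device received as secondary only. This concerns the analysis and leaves the care offered to refusers as it is.
- State that the randomisation table is retained as a patient-level list linked to the form by UHID.
- Add to the form: randomised arm and randomisation number; device actually fitted, with the posterior slab cast as its own entry; TCC refused (yes/no, date); any later device change (date and reason).
- For patients already enrolled, back-fill the arm from the table.
- Report the number of refusers.

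The cost is one form revision, a short addition to section 7 and minor back-filling, with no extra patients or procedures. The trade-off is that, with refusers kept in the TCC arm, the analysis may show a smaller difference between the devices. The device-received analysis can be set beside it, labelled as non-randomised.
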